# II. Glossary of terms and abbreviations

AE Adverse Event

ADE Adverse Device Event
AR Adverse Reaction
BP Blood Pressure

APR Annual Progress Report

DMEC Data Monitoring and Ethics Committee

eCRF Electronic Case Report Form

GCP Good Clinical Practice
ISF Investigator Site File

JRMO Joint Research Management Office

MHRA Medicines and Healthcare products Regulatory Agency

Participant An individual who takes part in a clinical study

QMUL Queen Mary University of London

REC Research Ethics Committee
RSI Reference Safety Information

SAE Serious Adverse Event

SADE Serious Adverse Device Event
SAR Serious Adverse Reaction
SDA Source Data Agreement

SUSAR Suspected Unexpected Serious Adverse Reaction
TAN Transcutaneous autonomic neuromodulation

TMF Trial Master File

TMG Trial Management Group
TSC Trial Steering Committee

USADE Unexpected Serious Device Event
WHRI William Harvey Research Institute

VANS v3.0 20.04.2023 Page 4 of 44

Chief Investigator name: [name]

# IV. Synopsis

Full title	Autonomic modulation by transcutaneous vagal nerve stimulation in acute ischaemic stroke requiring mechanical thrombectomy: a phase IIa, sham controlled randomised trial.				
Short title and / or acronym	VANS				
Sponsor	Queen Mary, University of London				
Device classification	Class IIa				
Medical condition or disease under investigation	Acute ischaemic stroke requiring mechanical thrombectomy				
Study design and methodology	Triple-blind, randomised controlled trial, single NHS -site				
Planned number of participants	36				
Objectives	To determine whether non-invasive transcutaneous autonomic neuromodulation results in lower blood pressure variability in the first 24 hours from the start of mechanical thrombectomy, as measured by coefficient of variation compared to the control treatment.				
Inclusion and exclusion criteria	Inclusion criteria:				
Investigational Device(s)	AffeX-CT/001				
Treatment duration	Approximately $1-3$ hours of treatment across two separate calendar days.				
Follow up duration	Seven days after index mechanical thrombectomy				
Total duration for participants	Four months				
Planned Enrolment Period	Six months				
End of Trial definition	When the last patient has completed their seven day follow-up				

#### 1.0 Introduction

#### **Background**

Loss of autonomic variability is strongly associated with adverse outcomes after ischaemic stroke. Removing blood clots from the brain by mechanical thrombectomy has revolutionised the management of stroke, but more than 50% of patients do not regain functional independence.(PMID:26898852) Blood pressure (BP) control is important, since low and high BP (BP variability) are strongly associated with poor patient outcomes after thrombectomy. (PMIDs:32961389;31964286) Current therapy centre son the use of anti-hypertensive medication, but these drugs do not address lability of blood pressure, often have poor adherence and can be difficult for patients after a stroke to use.

Autonomic dysfunction causes labile blood pressure. Intact autonomic function is required to control blood pressure and potentially improve recovery after stroke. Impairment of baroreflex autonomic function, due to reduced vagal activity is associated with extreme BP variability, leading to further brain injury and cardiovascular complications.(PMID:30371208) Reduced baroreflex control is related to poor patient outcomes after stroke, independent of absolute blood pressure.(PMID:19834010) Disrupted autonomic control also promotes infection, an important determinant of outcome.(PMID:26723020)

Reversing baroreflex and vagal dysfunction is, therefore, widely held to have the potential to improve cardiovascular control and patient outcome in this context. (PMID:19834010) Non-invasive peripheral neuromodulation restores autonomic control. Vagal nerve stimulation improves autonomic control and reverses baroreflex dysfunction (PMIDs:28949064) but this has previously required surgically implanted devices which are expensive and impractical in the context of acute stroke. Afferent Electronic have achieved the same effect as these implantable devices by non-invasive transcutaneous autonomic neuromodulation (TAN). We have used this simple, safe, hand-held, low-cost device to increase vagal activity and baroreflex sensitivity through non-invasive, painless stimulation of nerves located in the outer ear to control blood pressure.

We have demonstrated that baroreflex sensitivity can be increased at the bedside by TAN for 30 minutes following acute trauma (a patient group in whom baroreflex dysfunction also develops rapidly after injury) If this can be replicated in thrombectomy patients, it will aid recovery and rehabilitation through five complementary mechanisms where it has been clinically demonstrated that increasing vagal nerve activity:

- Restore baroreflex sensitivity;
- Increase blood flow to ischaemic brain tissue through vagal activation. (PMID:27357059);
- Dampen cerebral/systemic inflammation.(PMID:26723020);
- Reduce atrial fibrillation and myocardial injury,(PMIDs:5744003,22739118) which are common after stroke, and independently predict cognitive decline and cardiovascular mortality
- Allows immediate commencement of vagal nerve stimulation, which has recently been shown to enhance upper-limb rehabilitation. (PMID:33894832)

#### Efficacy/ Safety/ Tolerability

In a systematic review, no safety or tolerability issues were identified. In our recent study, 3/86 participants reported minor outer ear irritation; no major adverse events noted.

#### 1.2 Rationale for study design

Afferent Electronic's proof-of-concept data shows daily TAN reduces BP and BP variability lasting months drug-resistant several even in hypertensive (https://fundingawards.nihr.ac.uk/award/NIHR202116). In this proof-of-concept randomised shamcontrolled trial, this study will examine whether early TAN on presentation for mechanical thrombectomy improves autonomic function in patients with acute ischaemic stroke by reducing blood pressure lability. Better control of blood pressure early after ischaemic stroke is challenging with drug therapy, due to compliance and ability to ingest tablets. Our investigational device might be an improvement on currently available pharmacological treatments, since it is non-pharmacological and is readily accessible to all patients including after discharge from hospital. Compliance with device use can be monitored remotely to optimize therapeutic effect. We will examine the effect of TAN versus sham stimulation to ensure any effects are not attributable to placebo effect. The intervention has no impact on standard of care with other (pharmacological) therapies.

#### 1.3 Assessment and management of risk

The only established risk of the procedure is local skin irritation to the outer ear region. There is a theoretical risk of autonomic-induced cardiac arrhythmias, but there are no reports from an extensive literature search. The battery operated device bears no electrical risk.(PMID: 34801224) There are no other neurological side effects that have been reported. Our recent experience in 86 patients admitted with orthopaedic trauma who underwent TAN for pain control demonstrate no risks other than a local sensation of tingling in the outer ear and mild, inconsequential skin irritation that did not require any clinical intervention/therapy. The device is located well away from implanted pacemakers so pose no risk to other indwelling electrical devices. The overall risk-benefit ratio is very low, less than pharmacological interventions in stroke for blood pressure control.

VANS v3.0 20.04.2023 Page 8 of 44

# 2.0 Trial objectives

#### 2.1 Primary objective(s)

To determine whether non-invasive transcutaneous autonomic neuromodulation results in lower blood pressure variability during the first 24 hours from the start of mechanical thrombectomy, as measured by coefficient of variation compared to the control treatment.

#### 2.2 Secondary objective(s)

- Systolic blood pressure variability in the first 24 hours from the start of mechanical thrombectomy
- Diastolic blood pressure variability in the first 24 hours from the start of mechanical thrombectomy
- Heart rate variability in the first 24 hours from the start of mechanical thrombectomy
- Neurological recovery NIH Stroke
- Arrhythmias
- Myocardial injury

#### 2.2.1. Future research

Biomarkers for risk of infection

### 2.3 Endpoints

#### 2.3.1 Primary endpoint(s)

Coefficient of variation of systolic blood pressure measured in each patient during the first 24 hours from the start of mechanical thrombectomy.

# 2.3.2 Secondary endpoint(s)

- Systolic blood pressure variability from blood pressure measured in each patient during the first 24 hours from the start of mechanical thrombectomy.
- Disatolic blood pressure variability from blood pressure measured in each patient during the first 24 hours from the start of mechanical thrombectomy.
- Heart rate variability measured during each period of transcutaneous autonomic neuromodulation.
- NIH Stroke Scale (NIHSS) measured in each patient before the start of mechanical thrombectomy and 24 hours after the start of procedure.
- Clinically recorded arrhythmias in each patient during the first 24 hours after the start of mechanical thrombectomy.
- Absolute levels of serum high-sensitivity troponin-T levels measured before the start of the first transcutaneous autonomic neuromodulation and at the end of the second transcutaneous autonomic neuromodulation.

[figure not shown]

\* please see Appendix A for details on the assessment of primary and secondary outcomes

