#### Visit 3 (day after mechanical thrombectomy)

- The AffeX-CT device will be applied to each ear for typically one hour during this period
- Heart rate data will be captured by dedicated Holter monitors.
- Study data will be collected including concomitant medication and NIHSS will be recorded.
- Blood samples blood will be collected after the one hour stimulation period.
- Blood pressure data will be downloaded from the electronic health record and stored securely within QMUL/Barts Health NHS Trust for subsequent analysis.

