# 6.2 Schedule of assessment

Event/Visit	Screening	Day of MT*	Morning after MT	24 hours after MT*	Day 7 after MT*
Inclusion/exclusion	х				
Heart rate and blood pressure safety review		х		x	х
Informed Consent (professional/ personal)		х		х	
Informed Consent (patient)					х
Randomisation		х			
Heart rate		х	х		
Blood pressure		x		x	
Investigational procedure: TAN		х	х		
Medical record review	х	х		х	х
Trial blood sample		х		х	
Follow-up					х
Safety review		х		x	x

\*MT: Mechanical thrombectomy

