#### 10.11 Usage modifications and delays

• It is not envisaged that any modification in device usage or device itself during the conduct of the trial, except if a person develops local irritation/dermatitis which makes it difficult to use the clips to the ear. In that case, we will withhold treatment until the person can use the device or try to consider alternative options.

- There are no adverse events that could require the device usage to be modified.
- If participants develop cardiac arrhythmias, the device will not be used during that treatment period.
- Device usage will not be modified in accordance with the participants' results.
- The device setting/dose is modified to minimise local ear discomfort [i.e., current reduced on participant request].
- If the first treatment period is interrupted for clinical or device-related reasons, the Principal Investigator will be informed; proceeding with further treatment on the following day will be permitted as long as there are no [new] exclusion criteria met and after consultation with the Chief Investigator.
- The hardware of the device will not need to be modified during the study duration.

The most likely scenario we anticipate is the interruption of a treatment session. It is possible that patient stops the device or removes the electrode clips from the ear(s) before the duration of the session is complete. In that case, we will advise to reattach the device again for the remaining period and record the interruption. If they are not able to use the device for the full stimulation period, we will record a protocol deviation.

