#### 14.6 Procedure(s) to account for missing or spurious data

As the primary outcome uses routinely captured data stored by Barts Health EPR, there is minimal risk of missing blood pressure-related data. Heart rate data will be captured by dedicated Holter monitors provide by the Chief Investigator. Any missing data will not be inputed. Sensitivity analyses to assess the robustness of study results if there are missing primary outcome data will be undertaken. This pilot study will assess data completeness to inform decisions about missing data for a future main trial. Analysis will use all participants with available endpoint data. The level of missing data will be tabulated for each outcome, presenting the number of subjects with a data record and number with missing data, separately by trial arm. Each endpoint will be analysed on a complete case basis. For continuous variables, distributional assumptions will be hard to assess with the small sample size for this pilot study. However, if any continuous endpoint variables appear to seriously violate distributional assumptions or very extreme outliers observed, then non-parametric alternative approaches to analysis will be undertaken in such cases.

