# NIH Stroke Scale (NIHSS) measured before the start of mechanical thrombectomy and 24 hours after the procedure.

NIHSS will be assessed at the following time points by a member of the research team:

- any time point after admission to hospital but before induction of anaesthesia
- 24 hours from start of mechanical thrombectomy

Clinically recorded arrhythmias within the first 24 hours after the start of mechanical thrombectomy Defined as electrocardiograph evidence for cardiac rhythm as determined by the treating clinician either documented in the medical records and/ or recorded by a 12 lead ECG.

Absolute levels of serum high-sensitivity troponin-T levels measured before the start of the first transcutaneous autonomic neuromodulation and at the end of the second transcutaneous autonomic neuromodulation.

Additional blood samples to routine care will be collected to measure serum high sensitivity troponin-T (Elecsys, Roche Diagnostics) levels. Blood samples will be collected at any time after hospital admission but before the induction of anaesthesia and within two hours upon the completion of the second transcutaneous autonomic neuromodulation. The time of completion for transcutaneous autonomic neuromodulation is defined as when the device is switched 'on' and 'off' by a member of the research team. If blood samples are not collected, a protocol deviation will be recorded and data point classified as 'missing'.

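### The second troponin draw has no time of its own when session 2 is not given, so a patient still in hospital can be left without a post-treatment value or have the admission value counted as the peak

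*Protocol*

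**What the plan says.** **When the second sample is drawn.** Protocol 2.3.2 defines the endpoint as troponin "before the start of the first transcutaneous autonomic neuromodulation and at the end of the second transcutaneous autonomic neuromodulation". Appendix A places the second draw "within two hours upon the completion of the second transcutaneous autonomic neuromodulation". Section 6.1, Visit 3, states: "Blood samples blood will be collected after the one hour stimulation period". The 24-hour list in 6.6 also ties the sample to the end of stimulation. None of these gives a time for a patient who has no second session.

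The schedule in 6.2 differs. Its row "Trial blood sample" is marked under the 24-hour column, while the second stimulation is marked under the morning after. The SAP (Exploratory objectives) also sets the draws at admission and at 24 hours.

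**When it is not drawn.** Appendix A: "If blood samples are not collected, a protocol deviation will be recorded and data point classified as" missing. Section 14.6: "Each endpoint will be analysed on a complete case basis". SAP Appendix 1 instead takes the highest value within 24 hours, lets a single available value stand as the peak, and sets the outcome to missing only if both values are absent. SAP Table 6 shows a change from admission.

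**When session 2 may be absent.** Section 10.11: "If participants develop cardiac arrhythmias, the device will not be used during that treatment period". The same section withholds stimulation for ear irritation. The SAP (Exposure variables) gives the repeat session only while the patient is still at the treating hospital.

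**Analysis.** Protocol 14.2 and the SAP's general principles analyse patients with data in the arm to which they were randomised, whatever their compliance.

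**The concern.** An intention-to-treat comparison needs the outcome to be sought in the same way whether or not treatment was delivered. Here the instructions followed by the person drawing blood start the clock at the end of a treatment session. If that session does not happen, nothing says when to draw.

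The patients affected need not be typical. One who is in arrhythmia on the second morning may well have a higher troponin than one who is not. The protocol itself gives reasons why arrhythmia might differ by arm, in either direction: its Background expects vagal activation to reduce atrial fibrillation and myocardial injury, and 1.3 names arrhythmia as a theoretical device risk. Losing or replacing these values could therefore hide a harm or a benefit. The trial is also meant to inform a larger one (13.1), so a descriptive troponin result still carries weight.

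**Working it through.** **1. What happens to a patient in hospital with no session 2**

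| Text followed | Second draw due | Result |
|---|---|---|
| Protocol 2.3.2, 6.1, 6.6, Appendix A, 14.6 | No time stated | Missing if not drawn; patient dropped |
| Protocol 6.2 | 24 h column | Value exists if this table is followed |
| SAP Exploratory objectives and Appendix 1 | 24 h | If not drawn, admission value becomes the peak |
| SAP Table 6 | Not stated | Change from admission cannot be computed if not drawn |

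One patient can thus be missing, measured, or given a pre-treatment value, depending on the text used.

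**2. Are the two draw times the same?** Inputs from 6.7 and Appendix A: session 2 starts between 08:00 and 12:00, lasts 50 to 70 minutes, and the sample follows within 2 hours. Assume session 2 is on the next calendar day. For a thrombectomy starting at clock hour s:

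- earliest draw = 24 − s + 8 + 50/60 hours
- latest draw = 24 − s + 12 + 70/60 + 2 hours

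| Thrombectomy start | Draw, hours after start |
|---|---|
| 08:00 | 24.8 to 31.2 |
| 16:00 | 16.8 to 23.2 |
| 23:30 | 9.3 to 15.7 |

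The session-anchored draw is not a 24-hour draw. Counted from the start of thrombectomy, it can also fall outside the SAP's 24-hour window for the peak.

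**3. Numbers per arm.** The documents give no sample size or missing-data figure for troponin. The stated 36 belongs to the primary endpoint and can be reproduced: 2 × (1.960 + 1.282)² × 4²/5² = 13.45, so 14 per arm; 14/(1 − 0.05 − 0.05)² = 17.28, so 18 per arm and 36 in total.

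**4. Possible bias (assumed inputs).** Let m be the fraction of an arm without a second sample, D the extra troponin rise in those patients in SD units, and R = 1 SD the mean rise. Assume no true effect, so R is the same in both arms. The mean rise among sampled patients is then R − mD.

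- Complete case, active minus sham: −(mA − mS) × D
- Admission value as peak (rise counted as zero): (1 − mA)(R − mA·D) − (1 − mS)(R − mS·D)

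| mA v mS | D | Complete case | Single-value rule |
|---|---|---|---|
| 10% v 10% | 0.5 to 1.5 | 0 | 0 |
| 20% v 10% | 0.5 | −0.05 | 0.80 × 0.90 − 0.90 × 0.95 = −0.135 |
| 20% v 10% | 1.5 | −0.15 | 0.80 × 0.70 − 0.90 × 0.85 = −0.205 |
| 30% v 10% | 0.5 | −0.10 | −0.26 |
| 30% v 10% | 1.5 | −0.30 | −0.38 |

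Negative values flatter the active arm. At 10% active against 20% sham the signs reverse. In every unequal case shown, the single-value rule gives the larger bias.

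**5. Against the noise.** With all 18 per arm observed, the standard error of a mean difference is √(2/18) = 0.33 SD, so a 95% interval is about ±1.96 × 0.33 = ±0.65 SD. All the illustrated biases lie within it.

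**The case against.** A reader might infer that every patient without session 2 has no troponin outcome, and that the comparison is selected on events the device causes. The documents do not support that reading.

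- **The outcome is not always missing.** The SAP sets a 24-hour draw and keeps a single value as the peak. Appendix A treats an uncollected sample as a deviation, which suggests one is expected from everyone.
- **Arrhythmia.** The rule in 10.11 bars use only in the affected treatment period, so an arrhythmia in session 1 does not by itself cancel session 2. Section 1.3 calls the device risk theoretical, with no reports found.
- **Ear reactions.** The protocol reports 3 of 86 patients with minor irritation, about 1 in 36 at that rate (36 × 3/86 = 1.3). Nothing links this to troponin. For a patient withdrawn on this ground, section 7.0 stops further blood samples whatever the endpoint says.
- **Repatriation.** Nothing suggests the device causes it.
- **Weight.** Protocol 14.4 reports myocardial injury without a test, the SAP also lists it as exploratory, and Table 6 has no P column. Arrhythmia is an endpoint in its own right, and 14.6 tabulates missing data by arm.

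All of this narrows the point, but part remains. The SAP cannot recover a sample that the protocol gave no time to draw. A lone admission value is a pre-treatment measurement, and a patient who has one is not counted as missing for the peak, so the tabulation by arm would not show the problem. The SAP also names myocardial injury within a secondary outcome and promises an estimate, interval and p-value for each secondary outcome. Its sensitivity analysis for a missed repeat session covers only the primary outcome.

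**Conclusion.** The point holds in a limited form. The documents define the second troponin draw in conflicting ways, and the protocol's operative wording leaves no draw time when session 2 is not delivered. A patient still in hospital whose session is withheld (for example for arrhythmia that morning), refused or fails may be dropped, or may have an admission value counted as the outcome. Either makes a secondary outcome analysed as randomised depend on treatment delivery.

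The size is unknown. Bias between arms needs unequal withholding or a different case mix among those withheld; with equal withholding and similar case mix it is zero. The SD figures rest wholly on assumed rates and rises, and at 18 per arm they could not be told apart from chance. The case for change is that the definitions conflict and the remedy is nearly free, not that a material bias has been shown. The primary endpoint and the sample size of 36 are unaffected.

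**What to change.** 1. Use one troponin definition throughout: protocol 2.3.2, 6.1 Visit 3, 6.2, 6.6 and Appendix A; SAP Exploratory objectives, Appendix 1 and Table 6.
2. Give the second draw a time that applies to every participant still in hospital who has not declined sampling or been withdrawn, whether or not session 2 was delivered. A time counted from the start of thrombectomy would do, as would the morning slot in which session 2 was due.
3. Record the time from thrombectomy start to the draw and whether session 2 was given. Analyse as randomised.
4. Remove the rule that a lone admission value counts as the peak. Treat an absent post-treatment value as missing, and report such values by arm with reasons.
5. Reconcile section 7.0 (withdrawal for an inflamed or painful ear, with no further samples) with 10.11 (stimulation withheld), since they lead to different sampling for the same event.

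The cost is a wording amendment to the protocol and a SAP revision. No sample is added beyond the one already planned, and no treatment rule needs to change for the sampling fix. Two limits remain: some values will reflect one stimulation session only, which is what a comparison as randomised should include, and repatriated patients are not recovered.
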